11.4.3.1 Adverse Events

Adverse event incidence tables will present by system organ class (SOC) (sorted by internationally agreed order), high-level group term (HLGT), high level term (HLT), and preferred term (PT) sorted in alphabetical order for each treatment group, the number (n) and percentage (%) of patients experiencing an AE. Multiple occurrences of the same event in the same patient will be counted only once in the tables within a treatment phase. The denominator for computation of percentages is the safety population within each treatment group.

The proportion of patients with at least 1 TEAE, serious TEAE, and TEAE leading to discontinuation of the study will be tabulated by treatment group. In addition, TEAEs will be described according to maximum intensity and relation to the study drug. Serious AEs and AEs leading to study discontinuation that occur outside the treatment-emergent period will be summarized separately.

11.4.3.1.1 Adverse Events of Special Interest

The following summaries will be generated:

- Incidence of each AESI will be tabulated by treatment group.
- An overview summary of the number (%) of patients with
 - any AESI
 - any serious AESI (regardless of treatment-emergent status)
 - any treatment-emergent serious AESI
 - any AESI leading to death

- any AESI leading to permanent study drug discontinuation
- any AESI by maximum intensity, corrective treatment, and final outcome
- cumulative incidence at specified time points (K-M estimates at 1 week, 4 weeks, 12 weeks, 24 weeks and 52 weeks)

Definitions of AESIs and the method to identify AESIs will be specified in the SAP.

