10.6 SAFETY INSTRUCTIONS

10.6.1 Hypersensitivity

Allergic reaction is a potential risk associated with the administration of most therapeutic monoclonal antibodies.

Allergic reactions may be defined as allergic reaction-mediated signs and symptoms experienced by patients during or shortly after the pharmacologic or biologic agent given. These reactions may present in a variety of ways, including dizziness, headache, anxiety, dyspnea, hypotension, tachycardia, pruritus, rash, urticaria/angioedema, flushing, nausea, or vomiting. Anaphylaxis may represent the most severe form of infusion reaction, but these events may also occur via non-IgE mediated mechanisms (eg, anaphylactoid reactions), or may occur via other immune-mediated mechanisms (eg, cytokine-mediated). Refer to [Appendix L](#) “Definition of Anaphylaxis”, which describes the clinical criteria for the diagnosis of anaphylaxis.

Patients must be monitored for at least 30 minutes after each study-site administered investigational product administration for any signs or symptoms of a hypersensitivity reaction. Trained personnel and medications should be available to treat anaphylaxis or any severe allergic reaction if it occurs. Furthermore, the patients will be advised, when the IMP is administered at home, to self-monitor for potential signs and symptoms that may suggest a hypersensitive reaction for at least 30 minutes after administration.

Anaphylactic reactions or, systemic allergic reactions that are related to IMP and require treatment must be reported as an AESI (within 24 hours, for further details, see AESI definition in [Section 10.4.1.3](#) and [Appendix L](#)) and study medication should be permanently discontinued. Anti-drug antibodies and PK samples will be collected near the onset and resolution of the AESI for any additional analysis.

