- All treatment-emergent adverse event by primary SOC, HLG, HLT, and PT, showing number (%) of patients with at least 1 treatment-emergent adverse event sorted by the SOC internationally agreed order. The other levels (HLG, HLT, PT) will be presented in alphabetical order
- Number (%) of patients experiencing TEAE(s) presented by PT, sorted by decreasing incidence of PT
- All treatment-emergent adverse events by primary SOC and PT, showing the number (%) of patients with at least 1 treatment-emergent adverse event, sorted by the internationally agreed SOC order and by decreasing incidence of PTs within each SOC.
- Exposure adjusted incidence rate of all treatment-emergent adverse events by primary SOC and PT, showing the number of patients with at least 1 treatment-emergent adverse event per 100 patient-years
- All treatment-emergent adverse events regardless of relationship and related by primary SOC, HLG, HLT and PT, showing the number (%) of patients with at least 1 treatment-emergent adverse event, sorted by the internationally agreed SOC order. The other levels (HLG, HLT, PT) will be presented in alphabetical order
- All treatment-emergent adverse events by maximal severity, presented by primary SOC and PT, showing the number (%) of patients with at least 1 treatment-emergent adverse event by severity (ie, mild, moderate, or severe), sorted by the internationally agreed SOC order and by decreasing incidence of PTs within each SOC
- Number (%) of patients experiencing treatment-emergent adverse event(s) presented by primary and secondary SOC, HLG, HLT, and PT sorted by the internationally agreed SOC order. The other levels (HLG, HLT, PT) will be presented in alphabetical order
- Incidence rate of all common TEAEs (PT $\geq 2\%$) with $\geq 1\%$ higher incidence in one of the groups compared to any other by primary SOC and PT. The relative risk ratio of qualifying TEAEs along its 95% confidence interval will be presented.
- A listing of all treatment-emergent adverse events will be presented

Analysis of all treatment-emergent serious adverse event(s)

- All treatment-emergent serious adverse events by primary SOC, HLG, HLT, and PT, showing the number (%) of patients with at least 1 serious treatment-emergent adverse event, sorted by the internationally agreed SOC order. The other levels (HLG, HLT, PT) will be presented in alphabetical order

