- Number (%) of patients with any specific AESI leading to death
- Number (%) of patients with any specific treatment emergent AESI leading to permanent study drug discontinuation
- Number (%) of patients with any specific treatment emergent AESI by maximum intensity, corrective treatment, and final outcome
- Number of specific treatment emergent AESI adjusted by the exposure duration
- Number of patients with any specific treatment emergent AESI adjusted by the exposure duration
- Number of patients with any specific treatment emergent AESI adjusted by the exposure duration at risk. For each AESI, Kaplan-Meier estimates of cumulative incidence at Week 12, 24, 36 and 52 and K-M plot may be provided to depict the course of onset over time if the number of events is large enough
- Number (%) of patients with injection site reactions by the related injection
- Number (%) of patients with different number of injection site reactions

Analysis of pretreatment adverse events

- All pretreatment adverse events by primary SOC and PT, showing the number (%) of patients with at least 1 pretreatment adverse event, sorted by the internationally agreed SOC order and decreasing incidence of PTs within each SOC
- All serious pretreatment adverse events by primary SOC and PT, showing the number (%) of patients with at least 1 pretreatment adverse event, sorted by the internationally agreed SOC order and decreasing incidence of PTs within each SOC
- All pretreatment adverse events leading to permanent treatment discontinuation by primary SOC and PT, showing the number (%) of patients, sorted by the internationally agreed SOC order and decreasing incidence of PTs within each SOC
- All pretreatment adverse events leading to death by primary SOC and PT, showing the number (%) of patients, sorted by the internationally agreed SOC order and decreasing incidence of PTs within each SOC

If only a few patients have pretreatment adverse events leading to permanent treatment discontinuation, a listing will be presented instead of the summary table above.

Subgroup analysis for adverse events

Analysis of adverse events will be performed for below subgroups of interest based on safety population:

- Race (Caucasian/White, Black/of African descent, Asian/Oriental, all the other).
- Sex (Female, Male)
- Ethnicity (Hispanic, Not Hispanic)
- Baseline weight group (≤ 30 , > 30 kg)
- Baseline ICS level (Medium, High)

The subgroup analysis of adverse events includes:

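### The SAP drops the protocol's Week 1 and Week 4 Kaplan-Meier estimates for adverse events of special interest and makes the rest optional, without recording the change

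*Protocol*

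**What the plan says.** Protocol 11.4.3.1.1 opens its list of AESI outputs with "The following summaries will be generated". The last item on the list is "cumulative incidence at specified time points (K-M estimates at 1 week, 4 weeks, 12 weeks, 24 weeks and 52 weeks". The section leaves one matter to the SAP: "Definitions of AESIs and the method to identify AESIs will be specified in the SAP". It does not delegate the time points, or the decision whether to produce the estimates.

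SAP 2.4.5.1, under AESIs and other selected groupings, says "Kaplan-Meier estimates of cumulative incidence at Week 12, 24, 36 and 52 and K-M plot may be provided" and adds the purpose and condition "to depict the course of onset over time if the number of events is large enough". It gives no number for large enough.

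The same SAP section makes two commitments that bear on timing. One is a table, "Number (%) of patients with injection site reactions by the related injection". The other is "A listing of all treatment-emergent adverse events will be presented". Protocol 11.4.3.1.2 also promises a patient listing of AESIs.

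SAP 1.6 has two change tables. Table 2 lists major changes to the SAP, including added subgroup and exposure-adjusted analyses of adverse events. Table 3 lists changes from the analyses planned in the protocol, and its only entry is the removal of covariates from the FEV1 model.

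**The concern.** A promised safety output has become conditional and has lost its two earliest time points, and the SAP's own record of departures does not show it. For some AESIs early timing is informative. Protocol 10.6.1 describes allergic reactions as "signs and symptoms experienced by patients during or shortly after the pharmacologic or biologic agent given", so the first weeks of dosing are a natural place to look.

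Without the early points, a by-arm report could state how many children had, for example, a systemic hypersensitivity reaction without stating whether it came with the first doses or months later. An undefined event-count condition is most likely to remove the time course for the rarest categories.

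**Working it through.** No figure in the plan needs reproducing. The check is a comparison of texts, a dose count, and a search for other outputs that could fill the gap.

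**Step 1. Side by side.**

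| | Protocol 11.4.3.1.1 | SAP 2.4.5.1 |
|---|---|---|
| Time points (weeks) | 1, 4, 12, 24, 52 | 12, 24, 36, 52 |
| Status | committed | optional |
| Condition | none | enough events, no threshold |
| Logged as a departure | not applicable | no entry in SAP Table 3 |

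Two points are lost, one is gained, and a commitment becomes an option.

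**Step 2. Doses before each time point.** Protocol 8.1.4 gives dosing every 2 weeks, and the flow chart notes run it to Week 50. Scheduled doses fall at Weeks 0, 2, ..., 50, which is 50/2 + 1 = 26.

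- Before Week 1: Week 0, so 1 dose.
- Before Week 4: Weeks 0 and 2, so 2 doses (3 if the dose due that day is counted).
- Before Week 12: Weeks 0, 2, 4, 6, 8 and 10, so 6 doses (7 if the dose due that day is counted).

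The SAP's first point therefore pools 6/26 = 23% of scheduled doses (7/26 = 27% on the inclusive count). The visit window of ±3 days blurs the boundaries slightly but does not change the picture.

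**Step 3. Other outputs that could show early onset.**

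- *Injection site reactions by related injection* (SAP 2.4.5.1, committed). This resolves timing more finely than any Kaplan-Meier point, but only for injection site reactions.
- *Listings of treatment-emergent events and AESIs* (committed). These give individual timing but no by-arm summary.
- *Kaplan-Meier plot* (optional). It would show onset before Week 12 if produced.
- *Exposure-adjusted AESI rates* (SAP 2.4.5.1). These average over the whole period and cannot show early concentration.
- *Time to ALT, AST or bilirubin elevation* (SAP 2.4.5.3). This uses laboratory thresholds rather than AESI categories, and the first scheduled post-dose chemistry is at Week 12.

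For AESIs other than injection site reactions, none of these is a committed by-arm summary of onset by Week 1 or Week 4.

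**Step 4. How much censoring would matter early.** The sample size section assumes linear discontinuation of 20% at one year. On that assumption, loss by Week 1 is 20% × 1/52 = 0.4%, and by Week 4 it is 20% × 4/52 = 1.5%. Kaplan-Meier estimates that early would nearly equal simple proportions, so by-arm counts are an adequate substitute where events are few.

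**The case against.** The strongest reply is that this is a wording mismatch in a descriptive output. SAP 2.4.5 calls the safety analysis essentially descriptive and plans no systematic testing, so no error rate is affected. SAP 1.6 claims only to summarise major changes, and AESI time points need not count as major. If the plot is produced it shows early onset. If it is not, the stated reason is too few events, and the listings then suffice. All of this limits the severity. None of it supplies the missing by-arm summary or explains why a protocol commitment was relaxed.

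Four stronger readings are tempting, and the documents do not support them.

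- A reader might infer that early reactions to the first injections cannot be told apart from later ones at all. The by-injection table, the listings and the possible plot show otherwise.
- A reader might infer that the change hides a difference between on-site and home dosing. The visits listed for home administration start at Week 14, so a Week 12 estimate already falls near that boundary. Weeks 1 and 4 both lie inside the on-site phase.
- A reader might apply the timing language of Protocol 10.6.1 to severe injection site reactions. That language concerns allergic reactions only. Section 10.6.2, on severe injection site reactions, instead warns of a more intense reaction at a later injection.
- A reader might infer that the event-count condition will be judged with treatment results in view. The SAP does not say when it is judged, and it could be applied to blinded pooled counts.

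**Conclusion.** The point holds as a minor but real inconsistency. The SAP removes two time points that the protocol promised, makes the remaining output conditional on an unstated count, and does not record this in Table 3. The loss is confined to AESIs other than injection site reactions. For those, no committed by-arm summary separates onset within Week 1 or Week 4 from later onset, and the first planned point comes after 6 of 26 doses (7 if the dose due that day is counted).

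No efficacy conclusion or error rate is touched. The conclusion assumes that patient listings do not serve as a by-arm summary, and that an output described as optional may not appear.

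**What to change.** In SAP 2.4.5.1:

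- Give Kaplan-Meier cumulative incidence by arm at Weeks 1, 4, 12, 24, 36 and 52.
- Change *may* to *will* for every AESI category that reaches a stated minimum number of events. The sponsor should fix that number before unblinding.
- For categories below the minimum, show by-arm counts of patients with onset by each of those weeks.
- Record in SAP Table 3, with a reason, whatever still differs from Protocol 11.4.3.1.1. That would include the minimum count and the added Week 36.

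The cost is two more time points in an output already specified, a short count table and one log entry. The drawback is sparse estimates for rare categories, which the minimum count largely contains. Confidence intervals, or Kaplan-Meier estimates for categories with a single event, would go beyond what the protocol promises and are not needed to close the gap.

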11.4.3.1.2 Death

The following deaths summaries will be generated:

- Number (%) of patients who died by study period (treatment emergent period, on-study) and reasons for death summarized on the safety population by treatment received
- Death in nonrandomized patients or randomized and not treated patients
- TEAE leading to death (death as an outcome on the AE CRF page as reported by the Investigator) by primary SOC, HLG, HLT and PT showing number (%) of patients sorted by internationally agreed order of SOC and alphabetic order of HLG, HLT, and PT.

Patient data listings will be provided for all AEs, TEAEs, SAE, AEs leading to study discontinuation, AESIs and deaths.

11.4.3.2 Clinical Laboratory Evaluation, Vital Signs and Electrocardiogram Data

Results and change from baseline for the parameters will be summarized by treatment group for baseline and each post baseline time point, endpoint, minimum and maximum value. Summary statistics will include number of patients, mean, SD, median, Q1, Q3, minimum and maximum. The descriptive by visit analysis will be conducted from the baseline up to the scheduled evaluation visit for all patients disregarding the treatment status of the patients at each visit as long as their data is available.

The proportion of patients who had at least one incidence of PCSA at any time during the treatment-emergent period will be summarized by treatment group. Shift tables showing changes with respect to the baseline status will be provided.

Listings will be provided with flags indicating clinically out-of range values, as well as PCSA values.

11.4.3.3 Humoral Immune Response to Vaccines

For patients who receive vaccination, vaccine response parameters will be summarized by treatment groups with descriptive statistics. These parameters will be defined in the SAP.

11.4.4 Analyses of Systemic Drug Concentration, Anti-drug Antibodies, and Pharmacodynamic Variables

11.4.4.1 Drug Concentration Analysis

Concentrations of functional dupilumab in serum will be summarized using arithmetic and geometric means, SD, standard error of the mean (SEM), coefficient of variation (CV%), minimum, median, and maximum by treatment per visit.

Concentrations of functional dupilumab in serum will be used for population PK analysis by non-linear mixed effects modeling if warranted. Additional details of the analysis plan and the results will be provided in a separate document.

11.4.4.2 Anti-drug Antibodies Analysis

The incidence of positivity in the ADA assay will be assessed as absolute occurrence (n) and percent of patients (%), presented by treatment groups. Listing of ADA titer levels will be provided for patients positive in the ADA assay. Samples that are positive in the ADA assay will be further characterized for the presence of anti-dupilumab neutralizing antibodies.

Plots of concentrations of functional dupilumab will be examined and the potential influence of ADA on individual concentration-time profiles will be evaluated. Assessment of the potential impact of ADA on safety and efficacy may be provided.

Anti-drug antibodies at baseline will be summarized by:

- Number (%) of patients with a baseline sample negative in the ADA assay
- Number (%) of patients with a baseline sample positive in the ADA assay
- The summary statistics (including number, median, Q1, Q3, minimum, and maximum) of the titer for patients positive in the ADA assay at baseline

Anti-drug antibody incidence and titer will be provided for the following:

- Number (%) of patients negative in ADA assay at all times
- Number (%) of patients positive in ADA assay at any time
- Number (%) of patients with pre-existing positive response
- Number (%) of patients with treatment-boosted positive response
- Number (%) of patients with treatment-emergent positive response
- Number (%) of patients with transient treatment-emergent positive response
- Number (%) of patients with persistent treatment-emergent positive response
- Number (%) of patients with indeterminate treatment-emergent positive response
- The summary statistics (including number, median, Q1, Q3, minimum and maximum) of the peak post-baseline titer for patients with treatment-emergent positive responses

The minimum titer for samples positive in the ADA assay is based on the minimum required dilution of the assay. It will be classified as

- Low (Titer <1000)
- Moderate ($1000 \leq \text{Titer} \leq 10\,000$)
- High (Titer >10 000)

11.4.4.3 Pharmacodynamics and Phenotyping

The values to be used as baselines will be those collected at Visit 2 (Day 1). If any of the scheduled assessments on Day 1 are technically disqualified (eg, insufficient sample), then values determined in any other samples collected prior to the first IMP administration can be used as baseline.

For all parameters, raw data, absolute changes from baseline and percent changes from baseline will be summarized in descriptive statistics by treatment group and time point.

Summary plots (mean \pm SEM) on raw data, absolute changes from baseline and percent changes from baseline will be provided by treatment group.

As part of exploratory analysis, correlations between the baseline values for biomarkers and efficacy endpoints will be assessed.

11.4.5 Analyses of Patient Reported Outcomes (Health-related Quality of Life/Health Economics Variables)

Patient reported outcome variables collected in this study include the ACQ-IA questionnaire ACQ-7 score, PAQLQ(S)-IA score, PACQLQ score, and PRQLQ-IA score (in those with history of allergic rhinitis). The change from baseline for these endpoints will be analyzed using MMRM in the same fashion as for the endpoint of pre-bronchodilator % predicted FEV1. The covariates to be included are treatment, age, weight ($\leq 30\text{kg}$, $>30\text{kg}$), region, baseline eosinophil level ($<300\text{ cells}/\mu\text{L}$, $\geq 300\text{ cells}/\mu\text{L}$), baseline FeNO level ($<20\text{ ppb}$, $\geq 20\text{ ppb}$), baseline ICS dose level (medium/high), visit, treatment-by-visit interaction, corresponding baseline value and baseline-by-visit interaction. Descriptive statistics including number of patients, mean, standard error and LS means will be provided for each timepoint. In addition, differences in LS means, the corresponding 95% CI and the p-value will be derived from the MMRM model for comparison of dupilumab against placebo at each timepoint. Note that PRQLQ-IA score (in those with history of allergic rhinitis) will only be analyzed for patients with the history of allergic rhinitis.

11.5 INTERIM ANALYSIS

There is no interim analysis planned for this study.

11.6 PLANNED DATABASE LOCK

The database lock is planned based on the time when all randomized patients reach complete week 52 visit or discontinue from the study before week 52. Analyses will be based on all data collected up to this database lock and will be considered as the final analyses in the CSR (Clinical Study Report). Additional data between database lock and last patient completing last visit will be summarized in a CSR addendum

12 ETHICAL AND REGULATORY CONSIDERATIONS

12.1 ETHICAL AND REGULATORY STANDARDS

This clinical trial will be conducted by the Sponsor, the Investigator, and delegated Investigator staff and Sub-investigator, in accordance with consensus ethics principles derived from international ethics guidelines, including the Declaration of Helsinki, and the International Conference on Harmonisation of Technical Requirements for Registration of Pharmaceuticals for Human Use (ICH) guidelines for good clinical practice (GCP), all applicable laws, rules and regulations.

This clinical trial will be recorded in a free, publicly accessible, internet-based registry, no later than 21 days after the first patient enrollment, in compliance with applicable regulatory requirements and with Sanofi public disclosure commitments.

